4.7.3 Adverse events

All AEs either observed by the Investigator, or reported by the patient spontaneously or in a response to a direct question must be evaluated by the Investigator and will be recorded on the AE section of the CRF. As reported also in the [paragraph 4.3.3](#), if the patient discontinues for any reason (including discontinuation for pregnancy), with drug related adverse event ongoing at study end, he/she must be followed until resolution or stabilization of the event or until it is reasonable to consider the event not drug related any more or until the start of a new treatment, whichever occurs first.

In case of multiple reasons (e.g. patient withdraws the consent for toxicity), "adverse events" should be indicated as the primary reason whenever applicable. All relevant information related to the reason for treatment discontinuation including contributory factors must be included on the CRF.

A complete end of study visit must be performed by 7 days after the last drug intake for any patient permanently discontinuing study treatment. Should any drug-related AE still be ongoing beyond the last scheduled visit, this must be followed at subsequent follow-up visits until recovery. If a patient does not return for a scheduled visit, every effort should be made to contact the patient. In any circumstance every effort should be made to complete and report the observations as thoroughly as possible. All relevant information related to the reason for treatment discontinuation including contributory factors must be included on the CRF.

For AEs definitions, coding and reporting procedures see [paragraph 5](#).

4.8 Exploratory parameters

4.8.1 Evaluation of the effects of Givinostat on each single parameter of the clinico-haematological ELN response criteria

Each single parameter of the clinico-haematological ELN response criteria [21] (see [paragraph 4.6.1](#)) will be used to evaluate the effect of Givinostat in PV patients.

Only in case the enrolment in **Part A** is slow (i.e. **< 5 patients enrolled in 3 months**) and the eligibility for this part of the study may be expanded to all patients with cMPN, in this part of the study each single parameter of the ELN and EUMNET criteria will be used to evaluate the effect of Givinostat in ET and MF patients, respectively.

4.8.2 Evaluation of the effects of Givinostat on PD markers

To evaluate the effects of Givinostat on PD markers will be used mRNA analysis.

After evaluation of preliminary results and data exploration, some additional analyses may be performed to identify and quantify other molecular parameters of interest in term of improving of the knowledge of cMPN and the activity of the drug in these disorders.

4.8.3 Spleen size assessment

The spleen evaluation must be performed at the study centre according to the visit schedule outlined in the flow-chart ([Appendix A](#)).

To evaluate the effects of Givinostat on spleen size will be used MRI or CT scan.

The spleen evaluation will be performed during the study according to institutional guidelines and site-specific clinical practice (i.e. MRI or CT scan). For this reason, it is strictly recommended to the sites to provide the Sponsor or their designee with the local normal spleen values of the imaging performed for each patient according institutional guidelines and site-specific clinical practice (i.e. MRI or CT scan).

The same imaging technique and the same instrument to assess spleen dimension (i.e. MRI or CT scan) should be used on a patient throughout the study, if possible.

If possible, the spleen dimension will be evaluated as longitudinal diameter (hereafter “A”), antero-posterior diameter (hereafter “B”), transversal diameter (hereafter “C”) and Splenic Volumetric Index (hereafter “SVI”):

$$SVI = (A \times B \times C) / 27$$

4.8.4 Improvement of constitutional symptoms

To evaluate the improvement of disease-related constitutional symptoms, the Myeloproliferative Neoplasm Symptom Assessment Form (MPN-SAF) questionnaire (about 20 items) will be used in **Parts A** and **B**, in order to assess the most important clinical symptoms among patients with MPNs [24].

In addition, starting from MPN-SAF questionnaire, in **Part B** also the MPN-SAF Total Symptom Score [32] will be assessed as requested by the “**new**” ELN criteria (i.e. **revised** ELN response criteria) [32].

4.8.5 Reduction of the JAK2^{V617F} allele burden

To evaluate the reduction of the JAK2^{V617F} allele burden will be used the qRT-PCR. This molecular examination will be performed in a central laboratory ([Appendix E](#)).

After evaluation of preliminary results and data exploration, some additional analyses may be performed to identify and quantify other molecular parameters of interest in term of improving of the knowledge of cMPN and the activity of the drug in these disorders.

4.8.6 Reduction of the symptomatic treatment of pruritus in term of dosage and/or days of treatment

To evaluate the reduction of the symptomatic treatment of pruritus, the dosage and/or the days of treatment of each concomitant medication taken by the patient to treat this symptom will be used. This assessment will be performed using the data entered by Investigators in the specific section of the CRF.

4.8.7 Evaluation of preliminary efficacy according to the revised ELN criteria

Disease response will be evaluated also according to the following “**new**” ELN criteria (i.e. the **revised** ELN response criteria) **after 6 cycles** of treatment with Givinostat in **Part B** [33].

- **Complete remission:**
 1. *Durable* resolution of disease-related signs including palpable hepatosplenomegaly improvement, and *large symptoms improvement*, **and**
 2. *Durable* peripheral blood count remission, defined as HCT < 45% without phlebotomies, and PLT count $\leq 400 \times 10^9/L$, and WBC count < $10 \times 10^9/L$, **and**
 3. No progressive disease, and absence of any hemorrhagic or thrombotic event, **and**
 4. Bone marrow histological remission defined as the presence of age-adjusted normo-cellularity, and disappearance of tri-linear hyperplasia, and absence of grade > 1 reticulin fibrosis.
- **Partial remission:**
 1. *Durable* resolution of disease-related signs including palpable hepatosplenomegaly, and *large symptoms improvement*, **and**
 2. *Durable* peripheral blood count remission, defined as HCT < 45% without phlebotomies, and PLT count $\leq 400 \times 10^9/L$, and WBC count < $10 \times 10^9/L$, **and**
 3. No progressive disease, and absence of any hemorrhagic or thrombotic event, **and**
 4. No bone marrow histological remission defined as persistence of tri-linear hyperplasia.
- **No response:** any response that does not satisfy partial remission.
- **Progressive Disease:** transformation into post-PV myelofibrosis, myelodysplastic syndrome or acute leukemia (according to the IWG-MRT criteria for the diagnosis of post-PV myelofibrosis and according to WHO criteria for the diagnosis of myelodysplastic syndrome and acute leukemia).

Please note that according to the “new” ELN criteria (i.e. **revised** ELN response criteria) [33]:

- 1) Molecular response is not required for assignment as Complete Remission or Partial Remission. Molecular response evaluation requires analysis in peripheral blood granulocytes. Complete response is defined as eradication of a pre-existing abnormality. Partial response applies only to patients with at least 20% mutant allele burden at baseline. Partial response is defined as $\geq 50\%$ decrease in allele burden.
- 2) “*Durable*” is defined as lasting at least 12 weeks.
- 3) “*Large symptom improvement*” is defined as ≥ 10 points of decrease in MPN-SAF Total Symptom Score [32].

4.8.8 Evaluation of the effects of Givinostat on each single parameter of the revised ELN response criteria

Each single parameter of the “new” ELN criteria (i.e. **revised** ELN response criteria) [33] (see [paragraph 4.8.7](#)) will be used to evaluate the effect of Givinostat in PV patients in *Part B*.

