	
• Partial response: Patients who do not fulfil the criteria for complete response and
1. HCT <45% without phlebotomy, or2. response in 3 or more of the other criteria.• No response: any response that does not satisfy partial response. 
As an exploratory endpoint, disease response will be evaluated also according to the following “new” ELN criteria (i.e. the revised ELN response criteria) after 6 cycles of treatment with Givinostat in Part B.
 
• Complete remission:
1. Durable resolution of disease-related signs including palpable hepato-splenomegaly improvement, and large symptoms improvement, and2. Durable peripheral blood count remission, defined as HCT < 45% without phlebotomies, and PLT count $\leq 400 \times 10^9/L$, and WBC count < $10 \times 10^9/L$, and3. No progressive disease, and absence of any hemorrhagic or thrombotic event, and4. Bone marrow histological remission defined as the presence of age-adjusted normo-cellularity, and disappearance of tri-linear hyperplasia, and absence of grade > 1 reticulin fibrosis.• Partial remission:
1. Durable resolution of disease-related signs including palpable hepato-splenomegaly, and large symptoms improvement, and2. Durable peripheral blood count remission, defined as HCT < 45% without phlebotomies, and PLT count $\leq 400 \times 10^9/L$, and WBC count < $10 \times 10^9/L$, and3. No progressive disease, and absence of any hemorrhagic or thrombotic event, and4. No bone marrow histological remission defined as persistence of tri-linear hyperplasia.• No response: any response that does not satisfy partial remission.• Progressive Disease: transformation into post-PV myelofibrosis, myelodysplastic syndrome or acute leukemia (according to the IWG-MRT criteria for the diagnosis of post-PV myelofibrosis and according to WHO criteria for the diagnosis of myelodysplastic syndrome and acute leukemia).
--	--

Please note that according to the “**new**” ELN criteria (i.e. the **revised** ELN response criteria):

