4.5.2 Physical examination

Information about the physical examination must be present in the source documentation at the study site. Significant findings that are present prior to the start of study drug must be included in the Medical History section of the CRF or Current Medical Conditions section of the CRF. Significant findings reported after the start of treatment with the study drug that meet the definition of an AE must be recorded in the Adverse Event section of the CRF.

Study visit schedule and required evaluations and procedures to be performed at each study visit are described below and summarized in the flow-chart in [Appendix A](#). Methods of assessment of safety and efficacy are described in the [paragraph 4.6](#) and [paragraph 4.7](#) of the present protocol.

4.5.3 Spleen evaluation, PK and PD characterization, molecular examinations and bone marrow histological evaluation

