4.5.3.1 Spleen evaluation

The spleen evaluation must be performed at the study centre according to the visit schedule outlined in the flow-chart ([Appendix A](#)).

The spleen evaluation will be performed during the study according to institutional guidelines and site-specific clinical practice (i.e. MRI or CT scan). The same imaging technique and the same instrument to assess spleen dimension (i.e. MRI or CT scan) should be used on a patient throughout the study, *if possible*.

If possible, the spleen dimension will be evaluated as longitudinal diameter (hereafter “A”), antero-posterior diameter (hereafter “B”), transversal diameter (hereafter “C”) and Splenic Volumetric Index (hereafter “SVI”):

$$SVI = (A \times B \times C) / 27$$

No spleen evaluation will be performed in splenectomised patients.

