- Blood chemistry: ALT/SGPT, AST/SGOT, ALP, total bilirubin, LDH, creatinine, BUN or Urea (as per site-specific clinical practice; see [Appendix F](#) to convert Urea to BUN), glucose, Na, K, Ca, Cl, Mg, albumin, eGFR determination (according with the Mayo Clinic Quadratic Equation);
- ECG, QTc determination (according with Bazett's correction formula);
- Haematology: RBC count, HCT, Hb, MCV, MCH, MCHC, WBC count (full and differential), PLT count;
- Spleen evaluation by MRI or CT scan;
- Collection of a blood sample for the quantitative RT-PCR evaluation of JAK2^{V617F} mutational status on peripheral blood (PB) granulocyte;

- Assessment of disease-related symptoms using the MPN-SAF QOL Questionnaire [24, 32];
- Bone marrow histological evaluation (only for cycle 6) in patients who have consented to this optional exploratory research and that have not any medical contraindication to bone marrow sampling as judged by the Investigator;
- Therapeutic response evaluation according to the clinico-haematological ELN response criteria [21] (see [paragraph 4.6.1](#));
- Therapeutic response evaluation according to the “new” ELN criteria (i.e. **revised** ELN response criteria) [33] (see [paragraph 4.8.7](#)) (only for cycle 6);
- **Only for Cycle 3:** Givinostat administration;
- Used/unused/partially used Givinostat supply return and Givinostat accountability.

All phlebotomies performed in the first 3 weeks of treatment will be **not** counted to assess the therapeutic response.

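### In the revised-ELN criteria, Complete Remission asks for both resolution and improvement of palpable organ enlargement, while Partial Remission asks for resolution alone

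*Protocol*

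**What the plan says.** Section 4.8.7 lists four criteria for each remission category. Criterion 1 of both contains the words "resolution of disease-related signs including palpable hepatosplenomegaly", but they continue differently. For Complete Remission, criterion 1 requires durable "resolution of disease-related signs including palpable hepatosplenomegaly improvement" together with a large symptom improvement. For Partial Remission it requires durable "resolution of disease-related signs including palpable hepatosplenomegaly, and" the same symptom condition. The synopsis (Criteria for Response) repeats the difference: Complete Remission there reads "resolution of disease-related signs including palpable hepato-splenomegaly improvement", and Partial Remission again lacks the last word.

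Criteria 2 (blood counts) and 3 (no progression, no haemorrhagic or thrombotic event) are the same in both categories. Criterion 4 differs: marrow histological remission for Complete, persisting tri-linear hyperplasia for Partial. Durable means at least 12 weeks. Section 4.8.8 evaluates each single revised-ELN parameter separately.

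On measurement, section 4.8.3 says: "To evaluate the effects of Givinostat on spleen size will be used MRI or CT scan". The Part B screening list in 4.5.4.2.1 has "Spleen evaluation by MRI or CT scan", repeated at Day 28 of Cycles 3 and 6 and at End of Study. Section 4.5.3.1 adds: "If possible, the spleen dimension will be evaluated as longitudinal diameter", with two further diameters and a volumetric index. A physical examination is scheduled at screening, at every Day 28 visit and at End of Study (4.5.4.2.1 to 4.5.4.2.5). Section 4.7.2 calls it thorough and sends its results to the CRF. Section 4.5.2 says: "Information about the physical examination must be present in the source documentation at the study site", with significant findings going to the medical history, current conditions or adverse event sections. No procedure list names the liver or palpation.

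**The concern.** One sentence asks for resolution of a sign and, in the same clause, for its improvement. These are different thresholds. An organ that has shrunk but can still be felt has improved and has not resolved. Because the extra word stands only in the higher category, a literal programmer could let that patient pass criterion 1 for Complete Remission and fail it for Partial Remission, which inverts the order of the two categories. The word appears in both the synopsis and the body, so neither place corrects the other.

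At stake are the exploratory revised-ELN response rate after 6 cycles and the separate evaluation of criterion 1 under 4.8.8. A secondary matter is that criterion 1 is worded on palpation, while the protocol itemises no palpation variable to feed it.

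**Working it through.** The plan gives no figure for this point, so the check is a comparison of texts.

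**Step 1. Two readings of Complete Remission criterion 1.** Reading A: *resolution* governs and *improvement* adds nothing. Reading B: for palpable organ enlargement, improvement is enough. Partial Remission has only one reading.

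| Organ status, sustained 12 weeks | Complete, reading A | Complete, reading B | Partial |
|---|---|---|---|
| No longer palpable | met | met | met |
| Smaller, still palpable | not met | **met** | not met |
| Unchanged | not met | not met | not met |

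Only the middle row depends on the reading.

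**Step 2. Cross the middle row with criterion 4**, with symptoms and criteria 2 and 3 taken as met.

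- Marrow remission present: reading A fails Complete Remission at criterion 1. Partial Remission fails at criterion 1 and also at criterion 4, which requires that marrow remission be absent. Result: no response. Reading B gives Complete Remission.
- Tri-linear hyperplasia persists: Complete Remission fails at criterion 4 and Partial Remission at criterion 1. Result: no response on either reading.

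Two things follow. Under reading B, patients with the same organ status fall into complete remission or no response according to the marrow alone, and partial remission cannot be reached. And since a patient in marrow remission cannot drop back to Partial Remission, the ambiguous word changes the overall rate (complete plus partial) and not merely its split.

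**Step 3. Reach.** In the composite rate only patients with marrow remission, all other criteria met and organ enlargement improved but unresolved are affected. In the 4.8.8 analysis of criterion 1, any evaluated patient in the middle row is affected, whatever the marrow shows. Section 4.5.3.6 leaves patients who refuse marrow sampling out of both.

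**Step 4. Size per patient.** With all 28 Part B patients evaluated, one reclassified patient moves the rate by 1/28 = 0.0357, or 3.6 percentage points. With fewer evaluated the step is larger. The share of patients with palpable organ enlargement at baseline is not stated, so the total cannot be computed.

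**Step 5. Durability.** Cycles last 28 days. Cycle 3 Day 28 is nominally day 3 × 28 = 84 and Cycle 6 Day 28 is day 6 × 28 = 168. The gap is 168 − 84 = 84 days, or 12 weeks. So a finding of 12-week resolution at Cycle 6 needs to know the palpation status by about Cycle 3.

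**The case against.** The best defence of the wording is that both sentences are governed by *resolution*, that criterion 4 is the evident intended difference between the categories, and that the extra word is a drafting slip which a sensible reader would ignore. That is probably what was meant. It stands to this extent: the Complete Remission text is contradictory and not plainly looser. It does not remove the problem, because the text as written supports two scorings and the same word appears in both places.

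A reader might infer something stronger: that the spleen is measured only by imaging and the liver not at all, so that criterion 1 would be scored on a different quantity. The documents do not support this. A thorough physical examination is scheduled at every visit the criterion needs, and its results are to be entered in the CRF. No section says that MRI or CT scores criterion 1; the imaging statement in 4.8.3 belongs to the separate spleen-size endpoint. Evaluation of response under the revised criteria is itself a scheduled procedure at Cycle 6 and End of Study. The CRF is not at hand, so the absence of a palpation field cannot be asserted. What remains is narrower: palpation is not itemised as an efficacy variable. The route described in 4.5.2 captures significant baseline findings and new adverse events, and the disappearance of a finding is neither.

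**Conclusion.** The wording conflict is real and sits in the operative definition of the endpoint, in both 4.8.7 and the synopsis. It could misclassify a patient whose organ enlargement improved without resolving, in the revised-ELN rate and in the single-parameter analysis. The likely number of such patients is unknown; the step per patient is 3.6 percentage points on a denominator of 28.

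The consequence is limited. The endpoint is exploratory (3.3) and summarised descriptively (6.2.7.1). The primary clinico-haematological response uses normal spleen size, which imaging can score, and the Simon decision rule does not use the revised criteria. The conclusion assumes that the two categories were meant to differ by marrow histology alone, as the identical criteria 2 and 3 suggest. The published criteria that the protocol cites were not consulted. The palpation point is a supporting clarification and not a finding that the sign goes unmeasured.

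**What to change.** Delete *improvement* from criterion 1 of Complete Remission in 4.8.7 and in the synopsis, so that both categories ask for resolution in the same words. The sponsor should confirm this against the revised criteria it cites.

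As a supporting change, add one sentence to 4.8.7 saying that criterion 1 is judged by palpation at the physical examination already scheduled. Record palpable liver and palpable spleen status at screening, Cycle 3, Cycle 6 and End of Study, so that 12-week durability can be assessed. MRI or CT stays for normal spleen size in the clinico-haematological criteria and for the spleen-size endpoint.

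The cost is a one-word deletion in two places, one added sentence and a minor CRF update. No visit or procedure is added.

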4.9 Definition of end of the study

The end of the study (last patient last visit) will occur after all patients in whole study (*Part B*) have completed their last assessment as per protocol. Note that the analysis of the biological samples could be performed after the end of study due to scientific (i.e. after evaluation of preliminary results and data exploration, some additional analyses may be performed to identify and quantify other molecular parameters of interest in term of improving of the knowledge of cMPN and the activity of the drug in these disorders) or technical reason.

In any case, after the completion of the analysis all data will be formally reported in a Clinical Study Report and/or in a specific technical report.

5. ADVERSE EVENTS

The Investigator is responsible for the detection and documentation of AEs as defined in this protocol. AE data will be obtained at all study visits, based on information spontaneously provided by the patient and/or through questioning. Additionally, patients will be advised that they can contact the Investigator at any time to report or discuss AEs.

As reported also in the [paragraph 4.3.3](#), if the patient discontinues for any reason (including discontinuation for pregnancy), with drug related adverse event ongoing at study end, he/she must be followed until resolution or stabilization of the event or until it is reasonable to consider the event not drug related any more or until the start of a new treatment, whichever occurs first.

In case of multiple reasons (e.g. patient withdraws the consent for toxicity), “adverse events” should be indicated as the primary reason whenever applicable. All relevant information related to the reason for treatment discontinuation including contributory factors must be included on the CRF.

A complete end of study visit must be performed by 7 days after the last drug intake for any patient permanently discontinuing study treatment. Should any drug-related AE still be ongoing beyond the last scheduled visit, this must be followed at subsequent follow-up visits until recovery. If a patient does not return for a scheduled visit, every effort should be made to contact the patient. In any circumstance every effort should be made to complete and report the observations as thoroughly as possible. All relevant information related to the reason for treatment discontinuation including contributory factors must be included on the CRF.

